4.9.2 Study Treatment Discontinuation

Patients must discontinue MHAA4549A infusion and therefore treatment if they experience any of the following:

- Infusion related reactions

Patients must discontinue oseltamivir treatment if they experience any of the following:

- Pregnancy
- Serious skin/hypersensitivity reactions

The primary reason for study treatment discontinuation should be documented on the appropriate eCRF.

The IMC and SOC may recommend to permanently discontinue dosing for all patients within one or both study arms in the event of a general safety concern.

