4.5 CONCOMITANT THERAPY AND FOOD

4.5.1 Permitted Therapy

Concomitant medication includes any medication (e.g., prescription drugs, over-the-counter drugs, herbal or homeopathic remedies, nutritional supplements) used by a patient from 30 days prior to screening to the study completion/discontinuation visit. All concomitant medications should be reported to the investigator and recorded on the Concomitant Medications eCRF. For any NAIs (e.g., oseltamivir, peramivir, zanamivir, laninimavir) that have been taken prior to study drug therapy, the number of doses and duration of therapy must be recorded.

Patients who use oral contraceptives, hormone-replacement therapy, or other maintenance therapy should continue their use.

All therapies required for management of the patient's acute illness are permitted except for those listed below in [Section 4.5.2](#).

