4.5.2 Prohibited Therapy

Use of the following therapies is prohibited during the study and for at least 7 days prior to study treatment, unless otherwise specified below: probenecid, amantadine, or rimantidine

Use of other NAIs, including but not limited to oral oseltamivir, inhaled zanamivir, oral ribavirin, laninimivir, and peramivir, are prohibited during the study, but allowed up to 3 days (6 doses) prior to study treatment as outlined in the exclusion criteria. If oseltamivir resistance is highly suspected or identified during treatment then, following discussion with the sponsor medical representative, an alternative NAI to oseltamivir may be used.

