4.9 PATIENT, TREATMENT, STUDY, AND SITE DISCONTINUATION

4.9.1 Patient Discontinuation

Patients have the right to voluntarily withdraw from the study at any time for any reason. In addition, the investigator has the right to withdraw a patient from the study at any time. Reasons for withdrawal from the study may include, but are not limited to, the following:

- Patient withdrawal of consent at any time
- Any medical condition that the investigator or Sponsor determines may jeopardize the patient's safety if he or she continues in the study
- Investigator or Sponsor determines it is in the best interest of the patient

Every effort should be made to obtain information on patients who withdraw from the study. The primary reason for withdrawal from the study should be documented on the appropriate eCRF. However, patients will not be followed for any reason after consent has been withdrawn. Patients who withdraw from the study will not be replaced.

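### Minor: in protocol Version 3, no on-study rule allows a replacement neuraminidase inhibitor after a mandatory oseltamivir safety stop, because the only switch exception is for resistance

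*Combined protocol and SAP*

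**What the plan says.** All references are to protocol Version 3 (VHP Only) unless stated.

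- **Stop rule (4.9.2).** "Patients must discontinue oseltamivir treatment if they experience any of the following": pregnancy, or "Serious skin/hypersensitivity reactions". No substitute is named. Nothing in 4.9.2 or 4.9.3 takes a patient off study because oseltamivir has stopped.
- **Ban (4.5.2).** Other NAIs, in an open-ended list that includes zanamivir, peramivir and ribavirin, "are prohibited during the study, but allowed up to 3 days (6 doses) prior to study treatment as outlined in the exclusion criteria". Amantadine and rimantadine are barred separately.
- **The one on-study exception (4.5.2).** The condition reads: "If oseltamivir resistance is highly suspected or identified during treatment then". The permission attached to that condition reads: "following discussion with the sponsor medical representative, an alternative NAI to oseltamivir may be used".
- **General permission (4.5.1).** Therapies needed to manage the patient's "acute illness are permitted except for those listed below in" section 4.5.2. The same section adds: "All concomitant medications should be reported to the investigator and recorded on the Concomitant Medications eCRF".
- **Withdrawal (4.9.1).** One listed ground is "Investigator or Sponsor determines it is in the best interest of the patient".
- **Entry criteria (4.1.1, 4.1.2).** A negative pregnancy test is required. Pregnancy and known hypersensitivity to oseltamivir or its excipients are exclusions.

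The stop rule and the switch exception read the same in the original protocol (4.8.2 and 4.5.2) and in Version 2 (4.9.2 and 4.5.2).

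**The concern.** The protocol rests part of its ethical case on every patient receiving standard-of-care NAI treatment (1.3.2.1, 3.2.1, 3.2.3). Section 1.1 names zanamivir and peramivir beside oseltamivir as available agents. When oseltamivir becomes unsafe for a patient, 4.5.2 still bars those alternatives on study. It allows them when oseltamivir may not work, but not when it cannot be given.

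What is at stake is the care and follow-up of an occasional patient with severe influenza who has a serious reaction to oseltamivir. The site must leave the patient without an NAI, step outside the protocol to give one, or end the patient's participation. The documents give no reason for treating resistance and intolerance differently, so this looks like an omission.

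**Working it through.** The plan states no figure on this point, so the check is mainly a reading of the rules side by side, followed by a size per case.

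**1. Coverage.** Mandatory stop reasons in 4.9.2: 2 (pregnancy; serious skin or hypersensitivity reaction). On-study exceptions in 4.5.2: 1 (resistance). Overlap: 0 of 2.

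**2. Whether another section reopens the option.**
- 4.5.1 does not, because its permission excludes what 4.5.2 lists.
- 5.1 makes the investigator responsible for appropriate action but does not change 4.5.2.
- Since the patient stays on study after the stop, the ban continues to apply.

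**3. Routes that remain for giving an NAI.**
- A documented deviation (9.2).
- Withdrawal under 4.9.1 and treatment off study.
- A protocol change needed to eliminate an immediate hazard, which 9.5 lets the sponsor implement without prior approval.

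None of these is a standing permission. An antiviral that is neither an NAI nor named in 4.5.2 is not barred at all.

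**4. Doses affected, per patient.** The minimum course is 5 days, or 10 doses twice daily (3.1.1). The renal regimen is once daily (3.2.3, Table 2), so 5 × 1 = 5 doses.
- Twice daily, stop after dose k = 1 to 9: 10 − k = 9 down to 1 doses of the minimum not given.
- Once daily, stop after dose k = 1 to 4: 5 − k = 4 down to 1.
- Up to 6 doses of anti-influenza therapy may precede study treatment. A twice-daily patient may therefore have had between 1 + 0 = 1 and 9 + 6 = 15 doses when oseltamivir stops.

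**5. Follow-up, only if withdrawal is the route chosen.** Assume the early discontinuation visit falls on the day of the stop. Active AE reporting then ends at that visit and not at Day 60 (5.3.1).
- Stop on Day 1 to Day 5, the minimum course: 60 − 1 = 59 to 60 − 5 = 55 days early.
- Stop as late as Day 10, the limit of the supplied course (4.3.2.2): 60 − 10 = 50 days early. By then the minimum course is generally complete.

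This is not a total loss of safety information:
- 4.9.1 asks for every effort to obtain information, and bars follow-up only after consent is withdrawn.
- 5.4.4 keeps the open event followed.
- The sponsor is to be told of later deaths and SAEs (5.3.1), and of non-serious AESIs (5.5), that come to the investigator's notice. Section 5.4.2.2 words this duty more narrowly, for events judged related to study drug.

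**6. Weight of one case.** 1/334 = 0.30% of enrolled patients; 1/300 = 0.33% of evaluable patients (Version 3 totals, 6.1). No rate for either stop reason is given and none is assumed.

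**The case against.** The strongest reply concerns the status of the text. Version 3 is a regional amendment dated 25 September 2014. A Version 5 (Global) approved on 20 March 2015 follows it, but only its title page and the start of its amendment rationale are supplied. The visible part mentions no change to 4.5.2 or 4.9.2, but it is cut off. This stands: a reader might infer that the gap exists in the latest protocol, and the documents do not show that.

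Second, the triggers should be rare. Known oseltamivir hypersensitivity was added as an exclusion in Version 3, and a pregnancy test is required within 2 days before treatment. This also stands. What remains is chiefly a new serious reaction, an event 4.9.2 itself provides for.

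Third, 4.5.2 is loosely drafted. Its list of other NAIs names oral oseltamivir, the mandated background drug, and includes ribavirin. Its purpose may be only to bar non-study or add-on antivirals. That softens the literal reading but does not remove it, because the resistance clause implies that a switch otherwise needs permission.

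Fourth, keeping the background NAI uniform is a defensible aim, and whether to switch after a reaction or in pregnancy is clinical judgement. Both are fair. They support leaving the choice to clinicians, which the remedy does. They do not explain why resistance alone opens that choice.

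A reader might also infer that the protocol forces such patients to go untreated. It does not: the three routes in the working remain, and 8.1 commits the study to whichever standard protects the individual more.

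**Conclusion.** The gap is real in Version 3 and minor. Read as written, 4.5.2 and 4.9.2 give no on-study permission for a replacement NAI after a safety stop, so the site has to use a deviation, withdrawal or an immediate-hazard change. Very few patients should be affected. No alpha, power or sample-size figure depends on the point, and at about 0.3% of patients per case the effect on the primary estimate is negligible.

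Three stronger readings are tempting and unsupported:
- That the stop rule contradicts the 5-day minimum course. A safety stop is an ordinary exception to a planned course.
- That withdrawal removes 50 to 59 days of safety data. The figure applies only to active reporting, only if withdrawal is chosen, and only with the discontinuation visit on the day of the stop.
- That the trial's efficacy result is threatened. Nothing in the documents suggests enough cases for that.

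The conclusion rests on the Version 3 wording and on no later text having changed it, which cannot be checked here.

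**What to change.** Check the full Version 5 text first; if it already allows a switch after a safety stop, nothing is needed. Otherwise, in 4.5.2, insert after the resistance condition the clause *or if oseltamivir must be discontinued under Section 4.9.2*, so that the permission already given there ("following discussion with the sponsor medical representative, an alternative NAI to oseltamivir may be used") follows from either condition. Add a cross-reference to that sentence in 4.9.2. Whether to switch, and to which agent, stays with the investigator and the sponsor medical representative.

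The cost is one clause and one cross-reference. No new procedure or data item is needed, since concomitant medications are already recorded on the eCRF (4.5.1). A switched patient could stay on study for the Day 14, 30 and 60 visits. The downside is that a few patients may receive a different background NAI, which the concomitant-medication data will show.

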4.9.3 Study Completion/Early Discontinuation Visit

Patients who complete all study visits through Day 60 are considered to have completed study. All patients who discontinue from the study early will be asked to complete all assessments for the current visit day and for the early discontinuation visit without duplication. Please see Schedule of Assessments provided in [Appendix 1a](#) for assessments performed at the Study Completion/Early Discontinuation visit.

4.9.4 Study and Site Discontinuation

The Sponsor has the right to terminate this study at any time. Reasons for terminating the study may include, but are not limited to, the following:

- The incidence or severity of adverse events in this or other studies indicates a potential health hazard to patients.
- Patient enrollment is unsatisfactory.

The Sponsor will notify the investigator if the Sponsor decides to discontinue the study.

The Sponsor has the right to close a site at any time. Reasons for closing a site may include, but are not limited to, the following:

- Excessively slow recruitment
- Poor protocol adherence
- Inaccurate or incomplete data recording
- Non-compliance with the International Conference on Harmonisation (ICH) guideline for Good Clinical Practice (GCP)
- No further study activity (i.e., all patients have completed and all obligations have been fulfilled)

5. ASSESSMENT OF SAFETY

5.1 SAFETY PLAN

MHAA4549A is not approved and is currently in clinical development. Thus, the entire safety profile is not known at this time. The safety plan for this study is based upon preclinical data and the previous Phase 1 and Phase 2a (interim) studies and is designed to ensure patient safety. It will include specific eligibility criteria and monitoring assessments as detailed below and above in [Section 4.1](#).

The investigator, in consultation with the Sponsor, is responsible for assuring the safety of study participants who have entered this study and for taking appropriate action concerning any event that seems unusual, even if this event may be considered to be an unanticipated benefit to the study participant. The investigator will be responsible for a clinical assessment of the study participants before discharge from the study, and for the establishment of a discharge plan, if needed.

During the study, the incidence and nature of adverse events, serious adverse events, and laboratory abnormalities will be assessed. An ongoing blinded review of safety will be carried out by the Medical Monitor and a drug safety scientist. An unblinded review of safety will be performed on an ongoing regular basis by the IMC and SOC as described in the IMC and SOC agreement.

5.2 SAFETY PARAMETERS AND DEFINITIONS

Safety assessments will consist of monitoring and recording adverse events, including serious adverse events and non-serious adverse events of special interest; measurement of protocol-specified safety laboratory assessments; measurement of protocol-specified vital signs; and other protocol-specified tests that are deemed critical to the safety evaluation of the study.

Certain types of events require immediate reporting to the Sponsor, as outlined in [Section 5.4](#).

5.2.1 Adverse Events

According to the ICH guideline for GCP, an adverse event is any untoward medical occurrence in a clinical investigation patient administered a pharmaceutical product, regardless of causal attribution. An adverse event can therefore be any of the following:

- Any unfavorable and unintended sign (including an abnormal laboratory finding), symptom, or disease temporally associated with the use of a medicinal product, whether or not considered related to the medicinal product
- Any new disease or exacerbation of an existing disease (a worsening in the character, frequency, or severity of a known condition), except as described in [Section 5.3.5.9](#).
- Recurrence of an intermittent medical condition (e.g., headache) not present at baseline
- Any deterioration in a laboratory value or other clinical test (e.g., ECG, X-ray) that is associated with symptoms or leads to a change in study treatment or concomitant treatment or discontinuation from study drug
- Adverse events that are related to a protocol-mandated intervention, including those that occur prior to assignment of study treatment (e.g., screening invasive procedures such as biopsies)

Adverse events will be monitored throughout the entire study (enrollment through Day 60 or Early Discontinuation). If clinically significant signs or laboratory values are observed in a study participant, the investigator should repeat an assessment at the earliest opportunity. Only those events or laboratory values that exceed the level of clinical significance upon the repeat assessment will be considered an adverse event.

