5.2.3 Non-Serious Adverse Events of Special Interest (Immediately Reportable to the Sponsor)

Non-serious adverse events of special interest (AESI) are required to be reported by the investigator to the Sponsor immediately (i.e., no more than 24 hours after learning of the event; see [Section 5.4.2](#) for reporting instructions). Adverse events of special interest for this study include the following:

- Cases of potential drug-induced liver injury that include an elevated ALT or AST in combination with either an elevated bilirubin or clinical jaundice, as defined by Hy's law (see [Section 5.3.5.6](#))
- Suspected transmission of an infectious agent by the study drug, as defined below
 - Any organism, virus, or infectious particle (e.g., prion protein transmitting transmissible spongiform encephalopathy), pathogenic or non-pathogenic, is considered an infectious agent. A transmission of an infectious agent may be suspected from clinical symptoms or laboratory findings that indicate an infection in a patient exposed to a medicinal product. This term applies only when a contamination of the study drug is suspected.

- Adverse events associated with suspected cases of infusion-related reactions (IRR) which occur within 24 hours of study drug administration and may show the following signs and symptoms (for guidance on reporting AEs associated with IRR, see [Section 5.3.5.1](#) below):
 - Fever and/or shaking chills
 - Flushing and/or itching
 - Alterations in heart rate and blood pressure
 - Dyspnea or chest discomfort
 - Back or abdominal pain
 - Nausea, vomiting, and/or diarrhea
 - Various types of skin rashes
 - Anaphylaxis
- Anaphylaxis due to IV drugs most often presents with the following signs and symptoms:
 - Cutaneous symptoms: flushing, itching, urticaria, and/or angioedema (usually of face, eyelids, or lips)
 - Respiratory symptoms: repetitive cough, sudden nasal congestion, shortness of breath, chest tightness, wheeze, sensation of throat closure or choking, and or change in voice quality due to laryngeal edema
 - Cardiovascular symptoms: faintness, tachycardia (or less often bradycardia), tunnel vision, chest pain, hypotension, sense of impending doom, and/or loss of consciousness
 - Gastrointestinal symptoms: such as nausea, vomiting, abdominal cramping, and diarrhea

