5.3.5.1 Diagnosis versus Signs and Symptoms Infusion-Related Reactions

Adverse events that occur during or within 24 hours after study drug infusion should be captured as individual signs and symptoms rather than a diagnosis of allergic reaction or infusion reaction.

Other Adverse Events

For adverse events other than infusion-related reactions, a diagnosis (if known) should be recorded on the Adverse Event eCRF rather than individual signs and symptoms (e.g., record only liver failure or hepatitis rather than jaundice, asterix, and elevated transaminases). However, if a constellation of signs and/or symptoms cannot be medically characterized as a single diagnosis or syndrome at the time of reporting, each individual event should be recorded on the Adverse Event eCRF. If a diagnosis is subsequently established, all previously reported adverse events based on signs and symptoms should be nullified and replaced by one adverse event report based on the single diagnosis, with a starting date that corresponds to the starting date of the first symptom of the eventual diagnosis.

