5.3.5.4 Abnormal Laboratory Values

Not every laboratory abnormality qualifies as an adverse event. A laboratory test result must be reported as an adverse event if it meets any of the following criteria:

- Accompanied by clinical symptoms
- Results in a change in study treatment (e.g., dosage modification, treatment interruption, or treatment discontinuation)
- Results in a medical intervention (e.g., potassium supplementation for hypokalemia) or a change in concomitant therapy
- Clinically significant in the investigator's judgment (laboratory abnormalities should be repeated at the first opportunity and only considered clinically significant if they persist on repeat assessment)

It is the investigator's responsibility to review all laboratory findings. Medical and scientific judgment should be exercised in deciding whether an isolated laboratory abnormality should be classified as an adverse event.

If a clinically significant laboratory abnormality is a sign of a disease or syndrome (e.g., alkaline phosphatase and bilirubin 5× upper limit of normal [ULN] associated with cholestasis), only the diagnosis (i.e., cholestasis) should be recorded on the Adverse Event eCRF.

If a clinically significant laboratory abnormality is not a sign of a disease or syndrome, the abnormality itself should be recorded on the Adverse Event eCRF, along with a descriptor indicating if the test result is above or below the normal range (e.g., "elevated potassium," as opposed to "abnormal potassium"). If the laboratory abnormality can be characterized by a precise clinical term per standard definitions, the clinical term should be recorded as the adverse event. For example, an elevated serum potassium level of 7.0 mEq/L should be recorded as "hyperkalemia."

Observations of the same clinically significant laboratory abnormality from visit to visit should not be repeatedly recorded on the Adverse Event eCRF, unless the etiology changes. The initial severity of the event should be recorded, and the severity or seriousness should be updated any time the event worsens.

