5.3.5.5 Abnormal Vital Sign Values

Not every vital sign abnormality qualifies as an adverse event. A vital sign result must be reported as an adverse event if it meets any of the following criteria:

- Accompanied by clinical symptoms
- Results in a change in study treatment (e.g., dosage modification, treatment interruption, or treatment discontinuation)
- Results in a medical intervention or a change in concomitant therapy
- Clinically significant in the investigator's judgment. Abnormal vital sign values should be repeated at the first opportunity and only considered clinically significant if they persist on repeat assessment)

It is the investigator's responsibility to review all vital sign findings. Medical and scientific judgment should be exercised in deciding whether an isolated vital sign abnormality should be classified as an adverse event.

If a clinically significant vital sign abnormality is a sign of a disease or syndrome (e.g., high blood pressure), only the diagnosis (i.e., hypertension) should be recorded on the Adverse Event eCRF.

Observations of the same clinically significant vital sign abnormality from visit to visit should not be repeatedly recorded on the Adverse Event eCRF, unless the etiology changes. The initial severity of the event should be recorded, and the severity or seriousness should be updated any time the event worsens.

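### The repeat-assessment sentence in 5.2.1 conflicts with its own adverse event definition and with 5.2.3, 5.3.5.1, 5.3.5.4 and 5.3.5.5, so transient findings could go unrecorded

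*Combined protocol and SAP*

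**What the plan says.** Section 5.2.1 opens with the usual wide definition: "an adverse event is any untoward medical occurrence in a clinical investigation patient administered a pharmaceutical product, regardless of causal attribution". It then lists what this covers, including unfavourable signs and symptoms, and laboratory deterioration that comes with symptoms or alters treatment. None of this depends on the finding persisting.

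The last paragraph of 5.2.1 adds a repeat step: "If clinically significant signs or laboratory values are observed in a study participant, the investigator should repeat an assessment at the earliest opportunity". The next sentence makes the result of that step decisive: "Only those events or laboratory values that exceed the level of clinical significance upon the repeat assessment will be considered an adverse event".

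Four other sections govern the same findings:

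- 5.2.3 lists as adverse events of special interest "Adverse events associated with suspected cases of infusion-related reactions (IRR) which occur within 24 hours of study drug administration". They must reach the sponsor within 24 hours of the investigator learning of them. The listed signs include chills, flushing, and changes in heart rate and blood pressure.
- 5.3.5.1, to which 5.2.3 sends sites for these reactions, says: "Adverse events that occur during or within 24 hours after study drug infusion should be captured as individual signs and symptoms".
- 5.3.5.4 says: "A laboratory test result must be reported as an adverse event if it meets any of the following criteria". The criteria are accompanying symptoms, a change in study treatment, a medical intervention or change in concomitant therapy, and the investigator's judgment of clinical significance.
- 5.3.5.5 says: "A vital sign result must be reported as an adverse event if it meets any of the following criteria". It uses the same four criteria.

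In 5.3.5.4 and 5.3.5.5 the requirement to persist on repeat is attached only to the investigator's-judgment criterion. Sections 5.2.3 and 5.3.5.1 contain no repeat requirement.

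**The concern.** A definition decides what enters the adverse event form. If 5.2.1 is applied as written, a clinically significant sign or laboratory change that has settled by the time of the repeat is not an adverse event, even if it caused symptoms, needed treatment or interrupted dosing. Other sections require exactly such findings to be recorded. Sites cannot satisfy both, and about 170 planned centres may resolve the conflict differently.

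Safety evaluation is a stated objective, and 5.1 acknowledges that the product's full safety profile is not yet known. Section 6.5 builds its summaries by treatment group from the adverse events that were recorded. Anything screened out by the definition is missing from those tables. Infusion-related signs deserve particular attention because the protocol singles them out for expedited reporting and some of them can resolve quickly.

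**Working it through.** No arithmetic applies, and the plan gives no figure on this point to reproduce. The check is a comparison of texts, using Version 3, the latest full protocol supplied. The same sentence stands in 5.2.1 of the original protocol and of Version 2.

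**Step 1: scope of the repeat condition.**

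| Section | What it governs | Where persistence on repeat is required |
|---|---|---|
| 5.2.1, opening definition | all adverse events | nowhere |
| 5.2.1, closing sentence | events and laboratory values | as a condition of being an adverse event |
| 5.2.3 | suspected infusion-related reactions within 24 hours | nowhere |
| 5.3.5.1 | events during or within 24 hours after infusion | nowhere |
| 5.3.5.4 | laboratory values | 1 of 4 alternative criteria |
| 5.3.5.5 | vital signs | 1 of 4 alternative criteria |

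The closing sentence therefore agrees with the fourth criterion in 5.3.5.4 and 5.3.5.5 and conflicts with the other three in each (4 − 1 = 3). It also conflicts with 5.2.3, with 5.3.5.1 and with the definition it follows.

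**Step 2: three hypothetical findings, each normal on repeat.**

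1. *Blood pressure falls during the infusion, with symptoms, and the infusion is stopped.* Under the closing sentence of 5.2.1 this is not an adverse event. Under 5.3.5.5 it must be reported, both for the symptoms and for the change in study treatment. Section 4.9.2 itself ties infusion-related reactions to stopping the infusion, so the treatment-change criterion is a realistic route. If a reaction is suspected, 5.2.3 and 5.3.5.1 also apply.
2. *Low potassium is corrected with supplements before the repeat.* Under 5.2.1 this is not an adverse event. Section 5.3.5.4 uses potassium supplementation as its own example of an intervention that makes reporting mandatory. Here successful treatment is what makes the finding fail the 5.2.1 test.
3. *An isolated laboratory value with no symptoms, intervention or treatment change.* Here 5.2.1 and the fourth criterion of 5.3.5.4 agree that it is not an adverse event.

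The texts agree only in the third case, which shows how narrowly the closing sentence would have to be drawn.

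**Step 3: can the specific sections override the definition?** Not on the wording. Sections 5.2.2, 5.2.3, 5.3.1 and 5.3.5.1 all speak of adverse events, the term 5.2.1 defines. Read literally, a finding that fails the 5.2.1 test never becomes a serious event, an event of special interest, or an infusion-period event to be captured. Sections 5.3.5.4 and 5.3.5.5 do create a separate duty to report, but they contradict the closing sentence without saying which prevails.

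**Step 4: consequence for the analysis.** Section 6.5 summarises adverse events on or after Day 1 treatment by group, so findings excluded under 5.2.1 do not appear there.

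**The case against.** The best defence is that the closing sentence refers back to the one before it, which triggers a repeat only for signs or laboratory values. Symptoms such as itching, pain or nausea would then lie outside it. That narrower intent is plausible and limits the reach of the point. It does not remove the conflict: the operative sentence says events, and signs such as heart-rate and blood-pressure changes remain inside the trigger.

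A second defence is that a careful investigator will follow the specific rules. Sites are pointed to 5.3.5.1 for infusion reactions, 5.3.1 asks for all adverse events to be recorded, and stopping an infusion can meet a criterion in 5.3.5.5 by itself. Vital signs are also taken within an hour before and after the infusion, the most abnormal daily value is recorded when there are several, and 6.5 summarises changes from baseline. A transient vital-sign change may therefore reach the safety analysis by another route. This stands: it makes the loss a risk, not a certainty. It does not put the event into the adverse event tables.

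A reader might also infer that the undercount falls on the antibody arm and flatters it. The documents do not support that. They give no infusion-reaction rate by arm. Patients have severe influenza with oxygen or ventilatory support, so fever, fast heart rate and breathlessness can be expected in both groups, and blinded sites apply one rule to all patients.

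Finally, the current text may differ. The Version 4 (Russia Only) rationale lists a clarification about repeating abnormal assessments, and Version 5 (Global) says it consolidates elements of the country-specific amendments. Neither body is supplied, so whether the sentence survives is open.

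**Conclusion.** The inconsistency is established in every full protocol text supplied, through Version 3. Sites that apply 5.2.1 literally could omit transient, clinically significant signs or laboratory changes from the adverse event summaries, including infusion-related signs.

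The size cannot be estimated. The documents give neither the frequency of infusion reactions in this population nor the share that resolve before a repeat, and any number offered would be an assumption. A reader might infer that transient infusion reactions will not be counted at all. That goes too far, because several specific sections direct sites to record them.

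The conclusion rests on two conditions: that some sites would let the general sentence prevail over the specific ones, and that Version 5 has not already corrected it. The remedy is cheap enough to justify the change without a numerical estimate.

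**What to change.** First check whether 5.2.1 in Version 5 (Global) already incorporates the Version 4 clarification on repeat assessments. If it does and the conflict is gone, nothing more is needed.

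Otherwise reconcile the passages in one of two ways:

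- delete the closing sentence of 5.2.1; or
- limit it to isolated, asymptomatic laboratory or vital-sign values that need no intervention and lead to no change in treatment, matching 5.3.5.4 and 5.3.5.5.

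In either case add a cross-reference to 5.2.3 and 5.3.5.1, stating that infusion-related signs within 24 hours are recorded whether or not they persist. This concerns recording only and leaves patient management unchanged.

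The cost is a short wording amendment, a reminder to sites, and slightly more adverse events recorded.
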